5.1 Sub-studies

Seattle Children's Hospital R21

An R21-funded sub-study titled, “Differences in infecting and colonizing Enterobacteriaceae from short-course vs. standard therapy of pediatric UTI” is currently planned with collaborators at Seattle Children’s Hospital. This sub-study hypothesizes that both the antibiotic agent and the length of therapy will affect the patients’ indigenous flora and thus affect both the likelihood of recovering *E. coli* and/or *K. pneumoniae* from stool and the resistance phenotypes of the recovered isolates. The sub-study will utilize PCR- and sequence-based methods to characterize phylogenetic and resistance properties of the recovered isolates. The sub-study will also test the hypothesis that (1) *E. coli* and *K. pneumoniae* recovered from 2 or 3 stool cultures are more likely to be members of disease-associated subgroups within their respective species (*E. coli* phylogroups B2 and D, *K. pneumoniae* cluster Kpl); (2) treatment-susceptible strains recovered from cultures during treatment (culture #1 for 5-day arm; cultures #1 or #2, 10-day arm) are more likely to be members of disease-associated subgroups; (3A) treatment-resistant strains of either species are more likely than treatment susceptible strains to be recovered from cultures during treatment; and (3B) treatment susceptible strains of either species are more likely to be recovered from cultures during treatment in the AMC arm than in the TMP/SMX or CFX/CFD arms.

Carbapenem resistant enterobacteriaceae

For each enrolled research subject, the stool or perirectal swab collected at the Test of Cure visit will also be utilized to perform additional screening for the presence of carbapenem resistant enterobacteriaceae. The results of this additional screening will be used to determine the prevalence of colonization with carbapenem-resistant Enterobacteriaceae (overall and for specific pathogens) in ambulatory children after completion of treatment for UTI.

Microbiome pilot study

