The secondary outcome measures of this trial are provided above. A difference between the two arms with regards to asymptomatic bacteriuria, presence of clinical symptoms, and negative urine culture is not expected. No difference will mean that shorter courses of antibiotics for treatment are not inferior to long courses in eradicating bacteria from the urinary tract as well as impacting clinical symptoms. This analysis will be a conventional test for efficacy and will consist of a straightforward two-sample test for a difference between proportions, using a two-sided chi-square test at significance level of .05.

Sub-study Analysis:

Seattle Children’s Hospital R21

As previously noted, patient stool samples will be collected on 3 occasions. For primary analysis, cross-sectional analysis will be performed, i.e. looking at samples from one occasion at a time.

For each occasion, the following proportions will be summarized:

- 1) Among all patients, proportion of patients with *E. coli* detected, proportion of patients with *K. pneumoniae* detected, and same proportions within each treatment arm.
- 2) Among patients with *E. coli* detected, proportions of sub-type 0 or sub-type 1; among patients with *K. pneumoniae* detected, proportions of the two sub-types, and same proportions within each treatment arm.
- 3) Among patients with *E. coli* detected, proportions of treatment-susceptible *E. coli*; among patients with *K. pneumoniae* detected, proportion of treatment-susceptible *K. pneumoniae*; and same proportions for different treatment arms.
- 4) Among patients with *E. coli* detected AND treatment-susceptible, proportions of sub-type 1; among patients with *K. pneumoniae* detected AND treatment-susceptible, proportions of sub-type 1; and same proportions for different treatment arms
- 5) Among patients with *E. coli* detected proportion of treatment-resistant *E. coli*; among patients with *K. pneumoniae* detected, proportion of treatment-resistant *K. pneumoniae*; and same proportions within different treatment arms.

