After obtaining the proportions listed in (2) above, a binomial test will be used to determine whether the proportion of *E. coli* sub-type 1 (phylogroups B2 and D) is significantly larger than 50%. A chi-square test will also be used to test the differences in proportions of sub-type 1 across treatment arms. In addition, a multivariable logistic regression on presence of sub-type 1 strains will be conducted. The same approach will be used for *K. pneumoniae* sub-type 1.

For culture #1 (5-day treatment arm), or culture #1 or #2 (10-day treatment arm), the proportions of sub-type 1 will be tested using a binomial test, then a logistic regression will be used to examine the association between presence of sub-type 1 strains and treatment arms.

A chi-square test will be used to examine the difference in proportions estimated in (3) and (5) above. Logistic regression models will also be used for analysis.

Microbiome pilot study

We will preprocess all marker-gene microbiome sequencing data using the Quantitative Insights Into Microbial Ecology (QIIME) software package [PMID: 20383131]. This will include performing sequence quality filtering and demultiplexing of reads to separate sequences by sample. For taxonomic marker gene and RNA-Seq sequences, we will stitch overlapping paired-end reads together after demultiplexing using PANDAseq [PMID: 22333067]. We will then map marker gene reads to 97% operational taxonomic units (OTUs) using the Greengenes [PMID: 22134646] reference database and the USEARCH [PMID: 20709691] reference mapping software wrapped by QIIME. We will measure within-sample biodiversity (alpha diversity) based on these OTUs using whole-tree phylogenetic diversity⁵⁶ and the Greengenes reference phylogeny. To quantify

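### R21 sub-study: at stools 2 and 3 the planned shares are taken only among children whose stool grew the species, so a difference between arms cannot be read as an effect of treatment length on how many children carry resistant strains

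*Protocol*

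**What the plan says.** Protocol 12.4, Sub-study Analysis (Seattle R21), analyses one stool occasion at a time and lists these proportions, overall and by arm:

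- Item (1), recovery, is the only one taken over everyone: "Among all patients, proportion of patients with *E. coli* detected". No test is named for it.
- Item (2), sub-type: "Among patients with *E. coli* detected, proportions of sub-type 0 or sub-type 1", and likewise for K. pneumoniae.
- Items (3) and (5), the susceptible and resistant proportions, also use only children with the species detected. Item (5) ends: "and same proportions within different treatment arms".

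The tests follow. For sub-type: "A chi-square test will also be used to test the differences in proportions of sub-type 1 across treatment arms". For susceptibility and resistance: "A chi-square test will be used to examine the difference in proportions estimated in (3) and (5) above". The second sentence does not name the groups compared. Logistic regression is added for both.

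Protocol 5.1 states the sub-study's hypothesis: antibiotic agent and length of therapy will affect the patients' "indigenous flora and thus affect both the likelihood of recovering" the two species from stool, and also the resistance profile of the isolates that are recovered. The sub-study outcomes in Protocol 4.2.1 and 12.4 include presence of a treatment-resistant strain of each species, with no restriction to children in whom the species was found.

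SAP 4.2.4 repeats the detected-only denominators. It then says that the sub-study analyses are designed and carried out elsewhere, and leaves them there.

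**The concern.** Stools 2 and 3 are taken at the Test of Cure and Outcome Assessment visits, after the arms have diverged. Whether the species grows is by then an outcome of treatment. Children whose stool grew E. coli in one arm need not be comparable with those whose stool grew it in the other, so randomisation does not protect a comparison restricted to them.

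For resistance, the share among carriers rises whenever susceptible strains are lost, even if no additional child carries a resistant strain. It stays flat if both kinds of strain are lost in proportion, even though fewer children then carry resistant ones. A reader who takes a significant (or null) result as the effect of duration on resistant carriage could be wrong in either direction.

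**Working it through.** **The plan's own figure.** There is none to reproduce: the documents give no sample size, power, recovery rate or carriage rate for this sub-study.

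**Structure.** On one occasion and for one species, let r be the proportion of sampled children with a treatment-resistant strain, and s the proportion with susceptible strains only.

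- Recovery, item (1): r + s
- Resistant share among carriers, item (5): r / (r + s)
- Resistant carriage per sampled child: r

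If r is equal in the two arms and s is lower in one, the share is higher in that arm. If r and s fall by the same factor, the share does not move.

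**Assumed inputs.**

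- 300 stools per arm. The ceiling is 672/2 = 336, if every evaluable child gives a stool.
- r = 20% in both arms; s = 60% in the short-course arm.
- Two-sided 5% chi-square without continuity correction. The sub-study states no level; SAP 4.2.3 uses 0.05 for main-trial colonisation.

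**Case 1: equal resistant carriage, s = 60% v 30%.**

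- Carriers: 300 × 0.80 = 240 v 300 × 0.50 = 150. Resistant: 60 v 60.
- Shares: 60/240 = 25% v 60/150 = 40%.
- Pooled share: 120/390 = 0.308. Pooled SE = √[0.308 × 0.692 × (1/240 + 1/150)] = 0.0480.
- z = 0.15/0.0480 = 3.1.
- Unpooled SE = √(0.25 × 0.75/240 + 0.40 × 0.60/150) = 0.0488.
- Rejection ≈ Φ[(0.15 − 1.96 × 0.0480)/0.0488] = Φ(1.14) ≈ 87%.
- Over all sampled children: 60/300 v 60/300, difference 0, rejection about 5%.

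**Dependence on the assumption.** Simulation with 100,000 trials per setting, r = 20% in both arms:

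| s, short v standard | Shares | Rejection, 300 per arm | Rejection, 200 per arm |
|---|---|---|---|
| 60% v 30% | 25% v 40% | 87% | 72% |
| 60% v 40% | 25% v 33% | 47% | 33% |
| 60% v 50% | 25% v 29% | 14% | 11% |

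At 336 per arm, with r from 10% to 30% and unequal recovery, rejection ran from 9% (recovery 80% v 70%, r = 10%) to 100% (80% v 40%, r = 30%). With equal recovery it was about 5%. The all-children test stayed at 4.5% to 5.5% throughout.

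**Case 2: carriage differs but the share does not.** Take 336 per arm, with 30% resistant of 90% recovered (short course) v 20% of 60% (standard).

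- Shares: 101/302 = 33.4% v 67/202 = 33.2%, p = 0.95.
- All sampled children: 101/336 = 30.1% v 67/336 = 19.9%, p = 0.002.

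**Which stools.** Stool 1 is collected at enrolment, before study product starts, so study treatment cannot have altered its denominator. The point concerns stools 2 and 3.

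**The case against.** The strongest reply is that the sub-study also sets out to study the resistance profile of recovered isolates, which is conditional on recovery by definition. For that target, a rise in the resistant share from 25% to 40% is a true difference, and loss of susceptible strains under longer exposure may be the very selection of interest. This stands. A reader might take the 87% as the false-positive rate of the sub-study's own hypothesis test. It is one only if the result is read as resistant carriage per child.

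Further points on that side also stand:

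- The chi-square on (3) and (5) names no groups. It could compare arms, antibiotic agents (Protocol 5.1 also uses the word arm for agent), or susceptible with resistant recovery. Only the sub-type 1 test is expressly between treatment arms. The items are, however, tabulated by arm.
- The logistic models are described in terms of presence of sub-type 1 strains and are not stated to be detected-only.
- An all-children sub-type 1 test would differ between arms merely because longer therapy cleared the species, with no change in strain mix. A blanket replacement of the conditional tests is therefore not justified.
- Item (1) shows recovery by arm, so a careful reader could combine it with item (5). No test of the combination is planned.

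Secondary endpoint c does not fill the gap. It compares resistant colonisation per child without conditioning on recovery, but it does so in per-protocol populations, with a different definition of resistance, and part of it concerns emergent resistance. For the same reason, a disagreement between endpoint c and the sub-study could not be put down to the denominator alone, as a reader might suppose.

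**Conclusion.** The point holds as one of interpretation and of a missing test. At stools 2 and 3, a between-arm difference in the sub-type, susceptible or resistant shares describes recovered isolates in a subset formed after randomisation. It cannot be read as an effect of duration on how many children carry resistant strains. It can appear when carriage is equal and be absent when carriage differs.

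The size cannot be determined from the documents. They hypothesise that treatment length changes recovery but do not say by how much. The rejection rates of 87% and 14% rest wholly on the assumed carriage rates, and a false excess of resistance needs susceptible strains to be lost more than resistant ones. The documents do not support the stronger reading that the conditional analyses are invalid in themselves or that all of them should be replaced.

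The consequence is confined to the sub-study. Stool 1, the primary endpoint and secondary endpoint c are unaffected.

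**What to change.** In Protocol 12.4, R21 Sub-study Analysis, for stools 2 and 3:

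1. State that the between-arm test of treatment-resistant, and of treatment-susceptible, E. coli and K. pneumoniae uses all children with a stool cultured on that occasion as denominator. This matches the listed outcome of presence of a resistant strain, and it names the groups that the sentence on (3) and (5) leaves open.
2. Test item (1), recovery of each species, by arm.
3. Keep the shares among carriers, including sub-type 1, as analyses of recovered isolates. Show them beside the recovery rate and label them as not a randomised comparison.
4. If sub-type 1 is also shown over all sampled children, note that it combines recovery with strain mix.

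The cost is wording only. The counts already come from items (1) to (5), with no new samples or laboratory work. The downside is a few more rows and tests in an exploratory sub-study, and an all-children proportion that mixes recovery with phenotype, which is why the two need to be shown together.
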